3.3 Study Population and Groups/Arms

This study will recruit children aged 6 to 18, with 45 participants (15 in each group) diagnosed with CP, along with 15 TD participants.

3.4 Study Location

MRI scan will be performed in the radiology of Cook Children's. Behavioral tests, HD-EEG recordings, and rTMS sessions will be performed in the TMS room in Dodson.

3.5 Approximate Duration of Enrollment Period and Follow-Up

The study will last for 4 years.

3.6 Overview of Intervention and Administration

3.6.1 MRI Acquisition

MRI scans are needed to accurately localize neural activities from HD-EEG data and navigate specific motor regions for rTMS. All participants (CP and TD) will undergo an MRI scan to acquire T1-weighted images before the intervention. See 5.1.1. for details of the MRI.

3.6.2 Behavioral Assessment

The study utilizes several behavioral assessment tools to determine inclusion criteria. The Gross Motor Function Classification System (GMFCS) classifies the severity of movement disabilities in individuals with CP, focusing on their ability to perform gross motor functions like sitting and walking. Moreover, tests outlined in section 6.1 will be selected by each child's age and skill level.

Similar to the CP cohort, TD children will undergo behavioral tests. Their involvement is one-time and focused solely on providing comparative TEPs data

3.6.3 HD-EEG Recording

The HD-EEG setup involves placing electrodes across the scalp to monitor brain responses while applying rTMS. We will use a 64-channel system (eego mylab and Waveguard™ cap, ANT Neuro, Enschede, The Netherlands). This allows for precise mapping of the brain's electrical activity, enabling the investigation of changes in motor function and meta-plasticity induced by different rTMS frequencies in children with CP. See 5.1.2 for details of the HD-EEG.

3.6.4 rTMS

CP Participants in Experiment Group 1 will use rTMS using a figure-of-eight-shaped coil and rTMS stimulator (Nexstim, Finland) targeting the contralesional primary motor cortex. The intervention will consist of 10 sessions, each lasting 20 minutes, spread over four weeks. Each session will begin with priming: 10 minutes of 6-Hz rTMS at 90% of the resting motor threshold, delivered in two trains per minute (5 seconds per train with 25-second intervals between trains), totaling 600 priming pulses. This will be followed immediately by 10 minutes of 1-Hz rTMS at 90% of the resting motor threshold, delivered continuously without interruption, totaling 600 low-frequency pulses⁴⁷.

CP Participants in Experiment Group 2 will receive rTMS targeting the ipsilesional primary motor cortex. The intervention will consist of 10 sessions, each lasting 20 minutes, spread over four weeks. Each session will start with priming: 10 minutes of 6-Hz rTMS at 90% of the resting motor threshold, delivered in two trains per minute (5 seconds per train with 25-second intervals between trains), totaling 600 priming pulses⁴⁷. This will be followed immediately by 10 minutes of 10 Hz rTMS at 90% of the resting motor threshold, delivered continuously without interruption, totaling 2000 high-frequency pulses⁴⁸.

CP Participants in the Sham Group will receive rTMS by positioning the coil perpendicular to the scalp without delivering active stimulation, targeting both the contralesional and ipsilesional primary motor cortex. The intervention will consist of 10 sessions, each lasting 20 minutes, spread over four weeks. Each session will be divided into two parts:

- a. **Part 1:** 5 minutes of 6 Hz rTMS at 90% of the resting motor threshold, delivered in two trains per minute (5 seconds per train with 25-second intervals between trains), resulting in a total of 300 priming pulses on the contralesional primary motor cortex. This will be followed immediately by 5 minutes of 1 Hz rTMS at 90% of the resting motor threshold, delivered continuously without interruption, totaling 300 low-frequency pulses.
- b. **Part 2:** 5 minutes of 6 Hz rTMS at 90% of the resting motor threshold, delivered in two trains per minute (5 seconds per train with 25-second intervals between trains), resulting in a total of 300 priming pulses on the ipsilesional primary motor cortex. This will be followed immediately by 5 minutes of 10 Hz rTMS at 90% of the resting motor threshold, delivered continuously without interruption, totaling 1000 high-frequency pulses. See 5.1.3 for details of the rTMS.

TD children will complete a single baseline TMS-EEG session to measure TEPs (similar to the pre-intervention TMS-EEG in the CP cohort). This involves high-density EEG recording during single-pulse TMS to assess cortical excitability. The session will last approximately 60-90 minutes.

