Acoustic noise: The gradient field coils carry large, time-varying electrical currents during regular operation. The gradient coil in the static magnetic field is subject to force from these currents. The gradient coils produce an audible sound similar to a loudspeaker since they are not infinitely stiff and move slightly (about 100 microns) in response to these forces. This sound can be loud for some imaging sequences, such as echoplanar imaging, which this technique will use. The FDA has determined that a peak, unweighted sound pressure level of 140 dB represents a severe risk for acoustic noise in an MR system. This is not the sound level; the scan room is engineered to minimize acoustic reflections. For every MR scan, the MIC gives subjects headphones and earplugs, regardless of the system's sound intensity.

HD-EEG: HD-EEG has no known risks and is widely used in clinical and research settings. The non-invasive HD-EEG method is painless and uncomfortable. For all skin-contact physiological recordings, we shall use a hypoallergenic gel.

rTMS: Since TMS was first introduced in 1984, a number of side effects have been reported. The type of stimulation employed greatly impacts the likelihood of these side effects. To reduce the hazards as much as possible, the researchers will adhere scrupulously to all currently suggested safety precautions. When one pulse is administered at a time, as suggested in this study, there are no known negative effects or hazards associated with rTMS techniques. Hundreds of children have previously received a TMS or rTMS⁵⁸. Using this magnet can put a person in danger of having a seizure since it sends electromagnetic pulses through the brain. However, in the past, seizures have only happened in adult humans and animals when the magnet was employed for consecutive high-frequency impulses at a sustained level⁵⁹.

No children previously administered rTMS by the scientists experienced seizures or other notable neurologic problems. Numerous studies have shown that most children tolerate rTMS well⁶⁰⁻⁶². The various stimuli that can be used fall well within the boundaries of the most recent globally recognized safety standards. Risks, however, could include:

- a. **Headache and neck pain:** It is estimated that up to 20 out of every 100 TMS patients have Tightness in the neck muscles can cause headaches or neck pain. Acetaminophen (Tylenol®) quickly relieves discomfort in such situations.

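### The Group 2 10-Hz block gives four terms that cannot all hold: continuous 10 Hz for 10 minutes is 6000 pulses, not 2000, and sham Part 2 has the same factor of 3

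*Protocol*

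**What the plan says.** Section 3.6.4 describes each active session as a 10-minute 6-Hz priming block followed by a 10-minute main block. It gives the schedule as "The intervention will consist of 10 sessions, each lasting 20 minutes, spread over four weeks".

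- **Priming, both active groups:** 6 Hz, "delivered in two trains per minute (5 seconds per train with 25-second intervals between trains", with a stated total of 600 pulses.
- **Group 1 main block:** "10 minutes of 1-Hz rTMS at 90% of the resting motor threshold, delivered continuously without interruption, totaling 600 low-frequency pulses".
- **Group 2 main block:** "10 minutes of 10 Hz rTMS at 90% of the resting motor threshold, delivered continuously without interruption, totaling 2000 high-frequency pulses". Reference 48 is attached to this total.
- **Sham Part 2, after 5 minutes of priming:** "5 minutes of 10 Hz rTMS at 90% of the resting motor threshold, delivered continuously without interruption, totaling 1000 high-frequency pulses". The sham coil is held perpendicular to the scalp and no active stimulation is delivered.

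Section 3.6.4 refers to Section 5.1.3 for details of the rTMS. That section covers mapping, motor threshold, navigation, masking and the coil spacer. It gives no train length, inter-train interval or pulse count for 10 Hz.

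**The concern.** The Group 2 sentence fixes duration, frequency, mode of delivery and pulse total at once, and any three of them contradict the fourth. This block makes Group 2 the high-frequency arm, which is one side of the comparison in both primary objectives (Section 2.2). Section 11.4 requires the study to be conducted exactly as the protocol describes, yet an operator has to drop one term to run a session at all. If operators chose differently, the 15 children in that arm would not all receive the same intervention.

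Timing also bears on safety. Section 7.1.1 says of rTMS that "seizures have only happened in adult humans and animals when the magnet was employed for consecutive high-frequency impulses at a sustained level". Whether 10 Hz is given in short trains or unbroken for minutes is therefore a parameter the protocol should state without ambiguity.

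**Working it through.** **Inputs**, all from Section 3.6.4: the frequencies, durations, train pattern and pulse totals listed above, and 10 sessions of 20 minutes.

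**Rule.** Pulses = frequency × seconds of stimulation. For trains: frequency × seconds per train × trains per minute × minutes.

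**Totals that reproduce**
- Priming, active groups: 6 × 5 × 2 × 10 = 600 (stated 600).
- Group 1, 1 Hz: 1 × 600 s = 600 (stated 600).
- Sham priming, each part: 6 × 5 × 2 × 5 = 300 (stated 300).
- Sham Part 1, 1 Hz: 1 × 300 s = 300 (stated 300).

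**Totals that do not reproduce**
- Group 2, 10 Hz: 10 × 600 s = 6000 (stated 2000), a factor of 3.
- Sham Part 2, 10 Hz: 10 × 300 s = 3000 (stated 1000), a factor of 3.

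**Holding 2000 pulses and changing one other term in Group 2**
- Duration: 2000 / 10 Hz = 200 s = 3 min 20 s. The session is then 10 min + 3 min 20 s = 13 min 20 s, against 20 min stated.
- Frequency: 2000 / 600 s = 3.33 Hz, against 10 Hz stated.
- Delivery: the required on-time is 200 s out of 600 s, a duty cycle of one third, against continuous delivery stated.

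**Dropping the total instead:** 6000 pulses per session. Over 10 sessions that is 60,000, against 20,000 with the stated total.

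**Sham Part 2, holding 1000 pulses:** 1000 / 10 Hz = 100 s. The session is then 15 min + 1 min 40 s = 16 min 40 s. Spread evenly, 1000 / 300 s = 3.33 Hz.

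**Does the priming train pattern rescue the 10-Hz blocks?** No. At 10 Hz it gives 10 × 5 × 2 × 10 = 1000 in Group 2 and 10 × 5 × 2 × 5 = 500 in sham, half the stated totals.

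**Patterns that would fit 10 Hz, 10 minutes and 2000 pulses**
- 5 s on, 10 s off (four trains per minute): 10 × 5 × 4 × 10 = 2000; sham 10 × 5 × 4 × 5 = 1000.
- 10-s trains twice per minute: 10 × 10 × 2 × 10 = 2000; sham 10 × 10 × 2 × 5 = 1000.

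**The case against.** The arithmetic has no good rebuttal. The text is current and not redacted, the same factor of 3 appears in two separate blocks, and the protocol's own counting rule works everywhere else. Section 5.1.3 speaks of adjusting stimulation as data accrue, but it supplies no pattern. The objections with force concern what may be concluded.

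- **Which term is wrong.** A reader might infer that the continuous-delivery wording is proven to be the slip, because it matches the 1-Hz sentence, where it is correct. The text does not prove this. That wording appears in both 10-Hz blocks, just as the 10 Hz figure does. The sham total is exactly half of the Group 2 total in half the time, but it may have been copied from Group 2, so it is not independent support for 2000. The answer may also lie in reference 48, which is not at hand. An omitted train pattern remains plausible, as an inference only.
- **Size of the dose error.** A reader might infer that children will receive three times the intended pulses. The documents do not support that: 6000 arises only if an explicit total is ignored. Readings that keep the total deliver 2000 pulses and differ in timing.
- **Safety.** A reader might take Section 7.1.1 as evidence of seizures in children under this kind of stimulation. It confines past seizures to adults and animals. Epilepsy is also an exclusion (Section 4.2), and Section 7.1.2 provides monitoring and emergency procedures. These reduce the risk but do not define the dose.
- **Sham.** No active stimulation is delivered and coil clicks are masked (Section 5.1.3), so the sham discrepancy is secondary.

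**Conclusion.** The point holds, and the protocol must be corrected. The Group 2 10-Hz block is internally contradictory by a factor of 3, as is sham Part 2. The arm compared in both primary objectives cannot be delivered as written.

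If the stated total governs, the dose is 2000 pulses per session and 20,000 per course. What remains open is whether these come in trains over 10 minutes or unbroken in 3 min 20 s, or whether the frequency is wrong. The figures of 6000 per session and 60,000 per course belong to the least likely reading.

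The conclusion that the terms conflict needs no assumption beyond the stated numbers. Any statement about which term is wrong would need information the protocol does not give.

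**What to change.** The sponsor should confirm the intended 10-Hz parameters, check them against reference 48, and amend Section 3.6.4. Frequency, train length, inter-train interval, duration, pulse total and session length should agree for Group 2, and sham Part 2 should mirror them.

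- If 10 Hz, 10 minutes and 2000 pulses are intended, replace the continuous-delivery wording with a train pattern at a one-third duty cycle, chosen by the sponsor and justified for safety. Either pattern shown in the working would satisfy the totals in both arms; they are examples, not recommendations.
- If another term is wrong, correct that term and the session length with it.
- Do not resolve the conflict by adopting 6000 continuous pulses without an explicit safety justification.

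The cost is a protocol amendment with IRB approval before it is implemented, and possibly a revised consent form (Section 11.7). No extra participants, visits or procedures are needed.

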3.7 Randomization, Blinding and Any Stratification

After consent and assent are signed, only CP participants will be randomly assigned to the low-frequency, high-frequency, and sham groups using a computer-generated random sequence to ensure an even distribution of confounding factors. Blinding will be employed, with participants unaware of their group assignment to minimize bias. At the conclusion of their participation in the study, CP subjects and their families will be informed whether they were assigned to the active or sham rTMS group.

4. SELECTION AND ENROLLMENT OF SUBJECTS

4.1 Inclusion Criteria for CP

Individuals eligible to participate in this study must meet all of the following inclusion criteria to be registered in the study. Study treatment may not begin until a subject is registered.

- 4.1.1 Aged 6 – 18 years,
- 4.1.2 A confirmed diagnosis of CP by a specialized professional (pediatric neurologist, PM&R physician, neonatal developmental specialist, or neonatologist) is a prerequisite for participation,
- 4.1.3 Classified as high functioning (Level I, II, or III) according to the Gross Motor Function Classification System (GMFCS),
- 4.1.4 Age-appropriate ability to understand and comply with study procedure throughout the entire duration of the study,
- 4.1.5 Preserved vision and hearing (with or without correction).

4.2 Exclusion Criteria for CP

Individuals who meet any of the following exclusion criteria will not be eligible to participate in the study:

- 4.2.1 Syndromic or genetic associations,
- 4.2.2 History of trauma or brain surgery,
- 4.2.3 Inability to remain still,
- 4.2.4 History of Epilepsy,
- 4.2.5 Severe coexisting sickness or illness unrelated to CP or unstable medical conditions such as pneumonia,
- 4.2.6 Modified Ashworth Scale: Shoulder, elbow, and wrist scores more than 3,
- 4.2.7 Limb contractures caused by injury,
- 4.2.8 Severe movement disorders that prevent intentional limb movements, such as choreoathetosis, or ballismus,
- 4.2.9 Any congenital brain abnormality shown on a traditional brain MRI,
- 4.2.10A cast, splint, or recent surgery on the affected limb,

- 4.2.11 Botulinum toxin/phenol block applied to the afflicted limb within the last six months or anticipated during the research period,
- 4.2.12 Contraindications for rTMS include non-removable metallic objects close to a coil and implanted electronic devices, such as cochlear implants and pacemakers.

4.3 Inclusion Criteria for TD

- 4.3.1 Aged 6 – 18 years,
- 4.3.2 Age-appropriate ability to understand and comply with study procedure throughout the entire duration of the study,
- 4.3.3 Preserved vision and hearing (with or without correction).

4.4 Exclusion Criteria for TD

Individuals who meet any of the following exclusion criteria will not be eligible to participate in the study:

- 4.4.1 Syndromic or genetic associations,
- 4.4.2 History of trauma or brain surgery,
- 4.4.3 Inability to remain still,
- 4.4.4 History of Epilepsy,
- 4.4.5 Severe coexisting sickness or illness unrelated to CP or unstable medical conditions such as pneumonia,
- 4.4.6 Limb contractures caused by injury,
- 4.4.7 Severe movement disorders that prevent intentional limb movements, such as choreoathetosis, or ballismus,
- 4.4.8 Any congenital brain abnormality shown on a traditional brain MRI,
- 4.4.9 Contraindications for rTMS include non-removable metallic objects close to a coil and implanted electronic devices, such as cochlear implants and pacemakers.

4.5 Recruitment and Retention of Subjects

Children with CP will be recruited through neurology, NEST, stroke, neuropsychology, and physical therapy clinics. Participants from other studies who have consented to be contacted for future research will also be considered potential candidates.

Recruitment of TD children will be done via social media, our website (Research Center pages are being built), and tri-fold brochures at pediatric offices/neighborhood clinics. Participants will be compensated for their participation in the study. They will earn \$50 for each assessment session, and \$25 for every intervention session.

Diversity: The study will be open to all individuals who meet the inclusion criteria, regardless of race, ethnicity, or gender.

4.6 Consent Procedures

The patient will receive a thorough explanation of the study and have a chance to examine the permission form before enrolling in the research. The consent form must

include all currently required elements stipulated by the FDA, DHHS, and Cook Children's Institutional Review Board. The principal investigator (or a study team member) will acquire informed consent once this crucial information has been given to the patient and/or their parents/legally authorized representatives (LAR) and interest in participation has been verified. Following an informed consent conference, where the principal investigator (or a member of the study team leading the conference) will go over the goals of the study, the protocols to be followed, the length of participation, and the benefits and risks of participation as outlined in the consent form with the patient and/or their LAR, informed consent (and assent, if necessary) will be obtained. Once all of the patient's and/or parents/LAR's questions have been addressed and the person leading the consent conference is certain that the patient and/or parents'/LARs understand the ramifications of participation in the study, only then will the consent form be signed.

The subject and/or LAR will be asked to sign a consent document. In accordance with Cook Children's IRB policy, consent will be sought verbally from minors ages 8 to 12 and in writing from minors ages 13 to 17. Take note of the following: The IRB's standardized research permission and authorization template must be used to write consent, and the assent form must be written on the assent template. To comply with policy requirements, a script summarizing the proposed assent conference must be supplied (in language appropriate for the subjects' age range) if the assent is verbally acquired from subjects between the ages of 8 and 12. Additionally, the script must be developed using the IRB's assent template. Written copies of the informed consent and assent forms will be given to the patient and LAR. Copies of the original, signed consent and assent forms will be sent to the subject and/or LAR and kept in the patient's permanent medical record. To properly document consent that has been gained, a consent note will be filled out and placed with the completely executed consent document (or in the subject's study chart).

The investigator will adhere to Good Clinical Practice (GCP), ethical principles derived from the Declaration of Helsinki, and applicable regulatory requirements when obtaining and documenting informed consent. This study will also follow all applicable federal, state, and municipal laws, rules, and guidelines for conducting research on a vulnerable population.

5. STUDY INTERVENTIONS

The Principal Investigator will collect research material exclusively for research purposes, including demographic information, age, height, handedness, MR images, behavioral test scores, HD-EEG recordings, TMS data, and videos. No genetic testing will be conducted. With the consent of the participant's parent or guardian, video recordings will also be made during the assessments of MM. These recordings will be used strictly for educational purposes, research, and/or professional presentations and publications, separate from videos captured for research purposes. The faces of the

participants will appear in all video recordings. Videos utilized for research will have IDs to connect them to other data; optional videos used for publications, presentations, research, and/or teaching will not have identifiers except for displaying the participants' faces. Fourteen (14) visits will be required to collect the data: one for obtaining MRI, one for pre-intervention assessment, 10 for intervention, and two for conducting post-intervention and follow-up assessments, respectively. [Figure 1](#) shows the investigation workflow. The subject's medical record will only contain the results of the MRI and behavioral tests; all other testing is done only for research. When feasible, consent conferences will take place at routine clinic visits; if not, we will give our consent over the phone. There will not be a separate visit planned for the consent conference.

5.1 Interventions, Administration, and Duration

5.1.1 MRI

All participants (CP and TD) will undergo an MRI scan to acquire T1-weighted images before the intervention. This makes it possible for us to precisely pinpoint activity detected by the HD-EEG and to correlate the functional and anatomical characteristics of the brain more closely. The Cook Children's Radiology Department will provide the MRI data. In addition to being given the chance to see the scanner, participants who might find the close quarters within the machine uncomfortable will also be told where to press a button to halt the scan process. Younger children may sit inside the scanning room with a parent or guardian if they wear non-metallic clothing. To ensure that the scans obtained have minimal motion artifact, the researchers will advise parents/guardians to bring younger children during their regular naps, even if no sedation procedures will be utilized. Participants may also be permitted to watch a movie while the scan is taking place, and they will also receive earplugs to lessen scanner noise. Before entering the scan room, every participant will be inspected for metallic things, including jewelry, metallic implants, and anything considered dangerous near the MR scanner. Since an MRI scan doesn't use radiation, it has no known long-term negative effects. No medical diagnosis will be made using the MRI scan; it is being done solely for scientific reasons. If the participant's structural MRI is abnormal, either the attending radiologist or we will contact the child's Primary Care Physician (PCP) to discuss our findings. Every MRI will be included in the participant's medical file.

The MRI scan of any child who had an MRI before the intervention session will be obtained via the PACS system. We shall use template MRIs for data analysis if there isn't an available MRI and we cannot obtain MRI data from the child. This template MRI will come from an MRI database with templates of different age ranges. This MRI is required for two reasons: (i) HD-EEG data must be placed on the participant's 3D brain image to interpret the data, and (ii) MR images will be used for neuronavigation. Coregistration of HD-EEG data with structural MRI data is needed to pinpoint the origins of neural activity from HD-EEG recordings. Structural MRI (T1) will be included in

the imaging protocol. Cook Children's will use a 3T Siemens Tim Trio (Siemens Healthcare, USA) for scanning. The entire time spent gathering data will be about thirty minutes. The proposed structural sequence involves volumetric EPI navigators for real-time motion correction in a T1-weighted high-resolution magnetization-prepared rapid-acquisition gradient-echo (MPRAGE) acquisition. Additionally, we want to look into the quickest way to obtain various b-value data.

